4.3 End Points

For Cohort 1 - (14-day treatment interval)

Primary endpoint:

- Proportion of subjects exhibiting complete clearance of all treatable warts (baseline and new) at the EOS Visit (Day 84).

Secondary endpoints:

- Change from baseline in the number of treatable warts (baseline and new) at the EOS Visit (Day 84).
- Change from baseline in the percent of treatable warts (baseline and new) at the EOS Visit.

- Proportion of subjects exhibiting complete clearance of all treatable warts (baseline and new) at Visit 2, Visit 3, Visit 4, and over the duration of the study.

Exploratory endpoints:

- Percent reduction of all treatable warts (baseline and new) from baseline at Visit 2, Visit 3, Visit 4 and over the duration of the study.
- Change from baseline in the number of treatable warts (baseline and new) at Visit 2, Visit 3, Visit 4 and at the EOS Visit.
- Proportion of subjects exhibiting $\geq 50\%$ clearance of all treatable warts (baseline and new) at the EOS Visit as compared to baseline.
- Proportion of subjects who respond to treatment defined by a $\geq 50\%$ reduction in total wart area at EOS Visit compared to baseline.
- Proportion of subjects exhibiting reduction of at least 1 treatable wart from baseline at Visit 2, Visit 3, Visit 4 and at the EOS Visit.

For Cohort 2 – (21 +/- 4 -day targeted treatment interval) Primary endpoint:

- Proportion of subjects exhibiting complete clearance of all treatable warts, (baseline and new) at the EOT Visit (Day 84)

Secondary endpoints:

- Change from baseline in the number of treatable warts (baseline and new) at the EOT Visit (Day 84).
- Change from baseline in the percent of treatable warts (baseline and new) at the EOT Visit (Day 84).
- Proportion of subjects exhibiting complete clearance of all treatable warts, (baseline and new), at Visit 2, Visit 3, Visit 4 and over the duration of the study.

Exploratory endpoints:

- Percent reduction of all treatable warts (baseline and new) from baseline at Treatment Visit 2, Treatment Visit 3, Treatment Visit 4 and over the duration of the study.
- Change from baseline in the number of treatable warts (baseline and new) at Treatment Visit 2, Treatment Visit 3, Treatment Visit 4 and the EOT Visit (Day 84)
- Proportion of subjects exhibiting $\geq 50\%$ clearance of all treatable warts (baseline and new) at the EOT Visit (Day 84) as compared to baseline.
- Proportion of subjects who respond to treatment, defined as a $\geq 50\%$ reduction in total wart area at the EOT Visit (Day 84) as compared to baseline.
- Proportion of subjects exhibiting reduction of at least 1 treatable wart from baseline at Visit 2, Visit 3, Visit 4 and at the EOT Visit (Day 84).

- Proportion of subjects exhibiting complete clearance of all treatable warts (baseline and new) at follow-up visits on Day 105, Day 126 and Day 147.
- Percent reduction of all treatable warts (baseline and new) from baseline at follow-up visits on Day 105, Day 126 and Day 147.
- Change from baseline in the number of treatable warts (baseline and new) at follow-up visits on Day 105, Day 126 and Day 147

4.3.1 Safety

All subjects who meet the screening eligibility criteria for the study and receive at least one application of Study drug will be evaluated for safety. The following safety parameters will be assessed:

- Incidence of adverse events (AEs) throughout the study:
 - A subject-by-subject AEs data listing, including verbatim term, preferred term, treatment, severity, location and causal relationship to the Study drug, will be provided.
 - The number of subjects experiencing treatment emergent Adverse Events (TEAEs) and number of TEAEs will be summarized by treatment using frequency counts.
 - AEs will include all local skin reactions whether or not they are expected or related to Study drug mechanism of action.
- LSRs of all previously treated areas will be assessed at each Treatment Visit using the protocol specific ERT form.
 - Subjects will have reviewed and be given take home instructions on removal of the occlusive tape and also descriptions of the potential local skin reactions they might expect throughout the course of the study. Recommendations for wound care, when it is important to call their doctor, and instructions for whom to contact in an emergency are also included.
 - ERT assessments will be conducted at each Treatment Visit 1-4, in-person, prior to re-treatment. ERT phone calls will also be conducted at 24 hours and 7 days after Treatment Visits 1-4 to confirm removal of the occlusive tape, assess treatment response, document any local skin reactions and any medical interventions taken. ERT assessments will be conducted whether or not treatment is applied. Cohort 1 subjects that exhibit complete clearance prior to EOS, will not be required to return to the clinic until EOS Day 84. ERT phone calls will be scheduled and conducted at each two-week treatment interval until the in-person EOS visit or the subject reports recurrence or new warts that require an in-person assessment and treatment. Cohort 2 subjects will be required to return for each Treatment Visit until EOT as well as Follow-up Visits on Day 105, 126 and 147.
 - A LSR Guide for subjects with specific photos identifying the various skin reactions and examples of intensity will be reviewed at the clinic with the subject/guardian by the research team. This guide will be utilized for discussion during the ERT phone

assessments with the research team member. Should a subject report experiencing excessive blistering, ulceration, edema, pain or another adverse event needing physician assessment, they will be scheduled for an “Unscheduled” study visit and safety evaluation as soon as possible.

- Medical history, vital signs, and physical examinations:
 - Medical history, wart history, Fitzpatrick Skin Type and limited physical exams will be collected for each subject. A limited physical examination will be completed before the first treatment and at the EOS visit. Vital signs (temperature and heart rate) will be obtained before the treatment is applied at each visit and at the start of the Day 84 (EOS) Visit. Additional physical examinations will be performed when clinically warranted (e.g., subject reports symptoms classified as an AE requiring further evaluation).
- Limited physical examinations will be performed by a qualified medical practitioner at screening and at EOS visits. Height and weight will be recorded at the screening visit and at the EOS Visit. Unscheduled physical examinations will be performed when clinically warranted (e.g., if a subject reports signs or symptoms requiring further evaluation).
- Vital signs (e.g., heart rate and temperature) will be obtained at all Treatment Visits prior to treatment. A final assessment of vital signs will be obtained at the EOS Visit.
- If the subject discontinues the study prematurely (after the first treatment) for any reason, attempts will be made to encourage the subject/guardian to complete the EOS assessments.
- Subjects will be monitored for signs and symptoms of AEs throughout the study. All AEs (including LSRs) will be reported on the source and in the electronic case report form (eCRF), including seriousness, severity, action taken, and relationship to the Study drug. If AEs should occur, the first concern will be the safety of the subject.
- Assessment of LSRs will be recorded at each Treatment Visit using the protocol specific ERT form. Additional assessments will be conducted at 24-hours after treatment by phone contact using the ERT form. LSRs will be considered AEs even though some LSRs may be part of the normal response to treatment and correlated with efficacy. The following LSRs will be recorded: blistering, pain, pruritus, erythema, edema, erosion/ulcerations, flaking/scaling/dryness, scabbing/crusting and pigmentation changes (hyperpigmentation or hypopigmentation). These responses will be queried for duration and intensity. Scarring and ring warts will be evaluated in person by a qualified practitioner who is a trained member of the research team at in office Treatment Visits and the EOS visit.
- If the subject develops ring wart during the course of treatment, it is up to the investigators discretion to either continue treatment of that wart with VP-102, continue treatment of any other warts with VP-102 and discontinue treatment of the ring wart, or remove the subject from the study.
- Medical interventions taken throughout the course of the study prior to initial treatment and at 24-48 hours after treatment.

4.3.2 Efficacy

Efficacy parameters will be recorded for all enrolled subjects (Intent to treat) who receive at least one treatment application will be evaluated for efficacy. Clinical response to treatment will be evaluated at each scheduled visit until EOS by counting all treatable warts. Untreatable warts, if they arise, will be tracked and recorded.

4.4 Enrollment & Dropouts

Pre-study screening for eligibility (informed consent and assent [when applicable]), demographics, physical exam, prior and current concomitant medications, dermatologic exam with Fitzpatrick skin type, wart and medical history can occur up to 14 days before, or on the same day as the first Study drug application. The wart count (Cohort 1), measurements, location of all warts, ERT and photos must be repeated if not conducted on the same day as treatment. Subjects that do not continue to meet criteria at Treatment Visit 1 will be discontinued and treated at physician discretion per standard of care. Those subjects that meet the enrollment criteria will be treated with application of VP-102 at Treatment Visit 1. Treatment will continue with a minimum of 14 days between treatment until complete clearance or a maximum of 4 treatment sessions. The exact treatment interval will be determined by evaluation of the treatment site and take any ongoing LSRs into account. For subjects that achieve complete clearance or all treatable warts prior to Treatment Visit 4, ERT phone calls will be conducted at the required 2-week treatment intervals to assess the status of any AE's or skin reactions since the last visit and confirm there has been no recurrence in treated warts or new warts have developed. Subjects that report recurrence of, or presence of new warts, will be scheduled for a Treatment Visit per protocol. *(Sites should consider calling the subject a few days prior to the 2-week interval (e.g., 11 or 12 days) to ensure adequate time for scheduling assessment and treatment if needed.)*

The Day 84 EOS Visit will require a final assessment of ERT (for Cohort 1) and confirmation of the presence or absence of treated and untreated warts as well as the final size and diameter for any that are remaining. Subjects in Cohort 2 will participate in an in-person EOT evaluation at Day 84 (- 0/+ 8 days). A provider EOT Questionnaire will be completed at the EOT Visit. Cohort 2 subjects will continue in the study for 3 additional follow-up assessments on Day 105, Day 126 and Day 147. Each investigator conducting this final wart assessment, must be a study qualified member of the research team.

REPLACEMENT OF DROPOUTS

Subjects who do not complete the EOS/EOT assessment will be considered dropouts. Subjects who are enrolled in the study but never receive study drug will also be considered dropouts. Dropouts will not be replaced.

All treated subjects (including dropouts) will be evaluated in the intent-to-treat population. Those subjects who do not complete the full treatment due to lack of protocol adherence or who request to be discontinued from the study will be replaced. In the event a subject request to be removed from the study due to study-related adverse experiences or additional

spreading of disease, data will be collected and analyzed as a treatment failure and the subject will be replaced. Further discussion of how treatment failure will be utilized in analysis will be provided in the statistical analysis plan.

If a subject subsequently becomes able to provide informed consent (turns of legal age while on study) or a legally authorized representative is located after enrollment, information about the trial should be provided and procedures from the IRB/ethics committee will be followed. The subject or legally authorized representative can withdraw consent at any time during the study and for any reason without any penalty or changes to care. Data collected to the point that consent is withdrawn are still assessable by the principal investigator. If subjects do not want their data that has already been submitted or collected specimens utilized, they will need to submit a request in writing to the Investigator for removal of their information.

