Subjects in Cohort 1 that achieve complete clearance of all treatable warts prior to Treatment Visit 4, will receive ERT phone calls at the required 2-week treatment intervals to assess the status of any AEs or skin reactions since the last visit and confirm there has been no recurrence or development of new warts. In the event warts are present, the subject will be scheduled for a Treatment Visit per protocol. (*Consider calling the subject a few days prior to the 2-week interval (e.g., 11 or 12 days) to ensure adequate time for scheduling assessment and treatment if needed.*)

Subjects participating in Cohort 2, will be required to attend all visits regardless of whether they have achieved complete clearance of all warts at a previous visit. At these visits, Study drug application is not required if the warts have been clear for at least one follow up visit

and the investigator determines that additional treatment is not needed. Subjects participating in Cohort 2, that have completed their Day 84 EOT visit (- 0/+ 8 days), will be assessed at 3 additional follow-up visits conducted at Day 105, Day 126 and Day 147.

Subjects in Cohort 1 who are not assessed as 100% cleared of all treatable lesions at the Day 84, (EOS) visit will have completed the study and will be further treated per standard of care at their physician's discretion but may not be re-enrolled in this study. Subjects in Cohort 2 who are not assessed as 100% cleared of all treatable lesions at the Day 147; (EOS) visit will have completed the study and will be further treated per standard of care at their physician's discretion but may not be re-enrolled in this study

All subjects will receive application of the Study drug (VP-102) to common warts including a 1-2 mm margin of healthy, surrounding skin with an interval of at least 14 days in Cohort 1, and every 21 days in Cohort 2, until complete clearance of all treatable warts, or a maximum of 4 applications. Warts are to be treated and then occluded with transparent surgical tape (e.g.; 3M™ Blenderm™ brand) that will remain on overnight and removed just prior to the 24-hour ERT phone call.

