Subjects in Cohort 2 will undergo wart paring with a sharp surgical instrument (e.g., scalpel or flexible medical blade) to remove any adherent thick scale from a wart prior to application of Study drug. Wart paring is to be performed at any Treatment Visit when adherent thick scale is present, and the investigator considers that it can be safely applied. Paring should be conducted by a trained practitioner and in compliance with any local regulations and should be discontinued when it results in punctate bleeding or significant pain. Not all warts may require paring and if adherent scale is not present, then Study drug can be applied without paring. Subjects should be re-treated only after 14-days have elapsed in Cohort 1 and 17 days (i.e., 21 +/- 4 days) have elapsed in Cohort 2, but only after any LSR has resolved sufficiently to allow evaluation of the treatment site. Treatment should be administered within 4 days of becoming eligible due to resolution of LSRs.

For Cohort 1, subjects that achieve complete clearance of all treatable warts prior to the EOS visit, will return to the clinic for a final EOS visit at Day 84.

For Cohort 2 subjects are to attend all visits regardless of whether they have achieved complete clearance prior to and at the Day 84, (- 0/+ 8 days) EOT assessment.

Phone calls will be conducted at an interval of 24 hours and 7 days after each Treatment Visit (not "Unscheduled" Visits) to assess if there have been any adverse events or if new warts have occurred. Phone calls conducted outside of the required 24-hour and 7-day study ERT assessments should be documented in the subject's source note but are not required to be entered into the electronic data capture (EDC). All required study activities, including ERT evaluations, will be conducted per protocol. If new warts are identified during the course of the treatment period, they should be documented, evaluated and treated per manual of operations.

ERT will be performed in person, prior to each treatment. ERT phone calls will be conducted at 24-hours and 7 days after each Treatment 1-4 to assess treatment response, document any

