5.2 Dosing Instructions and Schedule

Upon activation, clinical sites will be provided with an initial supply of single-use applicators that each contains 0.45mL of the Study drug (VP-102). One applicator should be used to treat up to 6 common warts.

Following examination, subjects will receive application of Study drug to all warts with a minimum of 14 days (for Cohort 1) and 21 days (for Cohort 2) between treatment until

complete clearance or a maximum of 4 applications. The exact treatment interval will be determined by evaluation of the treatment site and take any ongoing LSRs into account.

Please see the Instructions for Use (IFU), located in the accompanied Investigational Brochure for step-by-step instructions.

Additional points to Consider:

Given the length of time or complexity it may take to treat all warts, investigators will assess in advance if subjects will be cooperative and able to sit still during the entire application of Study drug. Application may not be conducted over more than 1 visit. Subjects may be rescheduled for the first treatment as long as it is within the 14-day screening time period. Otherwise they will need to be rescreened and consent reviewed to participate.

Make sure the entire wart is covered including a 1-2 mm margin of surrounding, healthy skin. The Study drug must be completely dry before applying the occlusive tape. Tape MUST not be applied until the product is completely dry (approx. 2-5 min). Occlusive tape should be gently rubbed in order to maximize adherence to the treated area. The size of the piece of occlusive tape used is based upon investigator discretion provided that the entire wart is covered, and the tape size is deemed sufficient to maintain adherence for 24h. An adhesive bandage may be applied over the occlusive tape if needed for flexible areas such as fingers and joints to help keep it in place.

Observe subjects for 2-5 minutes after Study drug application or until the film is formed and totally dry. Subjects should refrain from touching, licking or biting treated skin or putting treated skin in or near any mucosal surface including the mouth, nostrils, eyes and anogenital area for up to 24 hours after treatment or until the Study drug is removed. Strongly urge subjects/guardians not to touch or wash the treated area for up to 24 hours.

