75-day treatment period for Cohort 2. It can sometimes be challenging to determine if a wart is completely clear 14 days post treatment due to ongoing local skin reactions. At any visit where the investigator is unable to evaluate or treat some warts due to ongoing local skin reactions, an “Unscheduled” visit should be documented. The timing of the next visit will be timed to correspond with the resolution of the local skin reaction. A Treatment Visit should be documented at every visit where any study drug is applied. Treatment should only take place at a visit when all warts are evaluable (i.e., not obscured by an ongoing LSR) and all warts that are not completely clear should undergo treatment with study drug. No partial treatment of warts is permitted. In instances where the clinician can adequately assess the treatment sites but is uncertain if residual wart is remaining, treatment should be applied, and the subject should return for evaluation per protocol. Treatment Visits are to take place in order (e.g., Treatment 1, Treatment 2, Treatment 3 and Treatment 4), although it is possible that some subjects will not receive less than 4 treatments within the 63-day (Cohort 1) or 75 day (Cohort 2) treatment period, due to the duration of post-treatment local skin reactions and this will not be considered a protocol deviation. No treatments should be administered after Day 63 (Cohort 1) or Day 75 (Cohort 2) without prior approval from the Sponsor.

ERT in-person safety assessments will be conducted during the initial treatment visit and at each subsequent Treatment Visits 2-4. In addition, safety follow-ups will include ERT phone assessments at 24 hours and 7 days after each treatment. During the Safety and Efficacy Evaluation Period, subjects will be scheduled every 14 days. For instances where all warts appear to be clear, yet the clinician is not certain if residual wart is remaining, treatment may be applied and the subject return for evaluation per protocol. Subjects that miss a treatment visit and are outside the 14-day study window, may return and be treated at the next available opportunity. AEs will be assessed at every study visit.

The EOS visit will be scheduled at 42 days after Treatment Visit 4 has been completed.

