For subjects that achieve complete clearance prior to Treatment Visit 4, ERT phone calls will be conducted at the required 2-week treatment intervals to assess the status of any AEs or skin reactions since the last visit and confirm there has been no recurrence in treated warts or new warts have developed. Subjects that report recurrence of, or presence of new warts, will be scheduled for a treatment visit per protocol.

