Subjects in Cohort 2 will undergo wart paring with a sharp surgical instrument (e.g., scalpel or flexible medical blade) to remove any adherent thick scale from a wart prior to application of Study drug. Wart paring is to be performed at any Treatment Visit when adherent thick scale is present, and the investigator considers that it can be safely performed. Paring should be conducted by a trained practitioner and in compliance with any local regulations and should be discontinued when it results in punctate bleeding or significant pain. Not all warts may require paring and, if adherent scale is not present, then Study drug can be applied without paring. Subjects should be re-treated only after 17 days (i.e., 21 +/- 4 days) have elapsed in Cohort 2, but only after any LSR has resolved

sufficiently to allow evaluation of the treatment site. Treatment should be administered within 4 days of becoming eligible due to resolution of LSRs.

For Cohort 2, subjects are to attend all visits regardless of whether they have achieved complete clearance prior to and at the Day 84, (+/- 8 days) EOT assessment.

Subjects in Cohort 2 will participate in an in-person EOT evaluation at Day 84 (+/- 8). A provider EOT Questionnaire will be completed at the EOT Visit. Cohort 2 subjects will continue in the study for 3 additional follow-up assessments at Day 105, Day 126 and Day 147. The follow-up visit window is +/- 4 days.

To assist the research team in the ERT phone calls, education materials in the form of a local skin reaction guide with specific photos identifying the various skin reactions and examples of intensity will be reviewed at the clinic with the subject/guardian by the research team. Should a subject report experiencing excessive blistering, ulceration, edema, pain or another adverse event needing physician assessment during the ERT call, they will be scheduled for an "Unscheduled" study visit and safety evaluation as soon as possible.

Subjects 18 and older must provide consent as required by the IRB before any study procedures are conducted. Parents or guardians must provide informed consent, and pediatric subjects older than 10 years must provide assent as required by the IRB before any study procedures are conducted. Subjects must meet all study eligibility criteria through a complete review of pertinent medical history, a dermatologic exam/wart count and physical examination.

4. Determination of Sample Size

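### The protocol gives conflicting re-treatment intervals and follow-up rules for Cohort 2; this affects compliance judgements, interim clearance rates and Per Protocol membership, but not the Day 84 primary endpoint

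*Protocol*

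**What the plan says.** **Interval.** Protocol section 4.4 states: "Treatment will continue with a minimum of 14 days between treatment until complete clearance or a maximum of 4 treatment sessions". Section 6.1 states: "During the Safety and Efficacy Evaluation Period, subjects will be scheduled every 14 days". Neither sentence names a cohort, although 6.1 elsewhere gives Cohort 2 both a plain 21 days and 21 days with a 4-day margin. Section 4.1, like the synopsis, permits re-treatment once "17 days (i.e., 21 +/- 4 days) have elapsed in Cohort 2". The SAP, which covers Cohort 2 only, repeats this in its Study Design section: "Subjects should be re-treated only after 17 days (i.e., 21 +/- 4 days) have elapsed in Cohort 2". Section 5.2 has the drug applied "with a minimum of 14 days (for Cohort 1) and 21 days (for Cohort 2) between treatment".

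**Follow-up after clearance.** For subjects clear before Treatment Visit 4, section 6.1 says that "ERT phone calls will be conducted at the required 2-week treatment intervals". It names no cohort, and section 4.4 carries the same rule. Under both, an in-person Treatment Visit is arranged only if the subject reports recurrence or new warts. Section 4.1 says that Cohort 2 subjects "will be required to attend all visits regardless of whether they have achieved complete clearance of all warts at a previous visit". Sections 4.3.1 and 6.2.3 and the footnotes to Table 2 agree with 4.1.

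**Rules that use these statements.** Section 8.1.3 lets a subject be discontinued for not being treated as Section 5 instructs. SAP section 6 removes subjects who miss required treatment visits from the Per Protocol population. SAP section 8.4.1 counts a subject with no clearance assessment in a visit window as not cleared at that visit. SAP section 8.4.2 carries the last wart count forward.

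**The concern.** Section 2.4 explains that the interval was lengthened for Cohort 2 so that skin reactions could resolve before evaluation, and that the study is meant to inform whether 21 days is suitable. Two sites could read different sections, both believe they are compliant, and treat and observe Cohort 2 differently. Compliance would then be judged against one section while sites follow another. A cleared subject could also be recorded as not cleared at an interim visit because the site made a phone call that the protocol text appears to allow.

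**Working it through.** **1. The plan's own figure.** Four applications have three intervals. Taking the upper edge of the window, 3 × (21 + 4) = 75 days, which reproduces the stated Cohort 2 treatment period. The lower edge is 21 − 4 = 17 days, the figure in section 4.1. The 75 days agree with the upper edge but do not settle the minimum.

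**2. Intervals set side by side.**

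| Actual interval (days) | 4.4 and 6.1, unlabelled (14) | 4.1, synopsis, SAP (17) | 5.2 (21) |
|---|---|---|---|
| 14–16 | meets | below | below |
| 17–20 | meets | meets | below |
| 21–25 | meets | meets | meets |

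The middle row is the practical conflict: it complies with 4.1 and the SAP but departs from Section 5, which 8.1.3 cites.

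**3. A cleared Cohort 2 subject followed by phone.** The SAP windows are Day 21 (11–31), Day 42 (32–52), Day 63 (53–73) and EOT (74–94). Suppose the subject is clear at Treatment Visit 2, near Day 21, and is then phoned under 4.4 or 6.1 until Day 84. Table 2 schedules no wart measurement at a phone call, and section 6.1 provides for a wart count by phone only in Cohort 1.

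- Day 42 and Day 63 windows: no assessment, so not cleared at either (SAP 8.4.1).
- Wart count in the same windows: zero carried forward (SAP 8.4.2). The subject would have no warts in one table and be not cleared in another.
- EOT window: assessed in person, because section 4.4 itself keeps the in-person Day 84 visit for Cohort 2.

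A subject first clear at Treatment Visit 3 would lose only the Day 63 window.

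**4. Size.** With about 35 subjects in the denominator, one such subject lowers a by-visit clearance rate by 1/35 = 2.9 percentage points; three lower it by 3/35 = 8.6 points.

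**5. Effect of spacing on the windows.** Visits every 14 days fall on Days 14, 28 and 42. The first two share the Day 21 window and the Day 63 window is empty. Day 63 is also empty at exactly 17 days (17, 34, 51) and at 25 days (25, 50, 75, the last falling in the EOT window). Intervals of 18, 20 or 21 days fill every window. Counting the first treatment as Day 1 gives the same pattern. Part of this comes from the windows themselves, so reconciling the interval text would not remove it.

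**The case against.** The strongest reply is that the 14-day and phone-call sentences are leftover Cohort 1 text that no site would misread. Cohort-specific statements elsewhere consistently give Cohort 2 an interval of 21 days or 21 ± 4. In-person attendance is stated repeatedly, and the parallel phone-call text in the synopsis and section 6.2.3 is limited to Cohort 1. Section 6.1 also places EOS 42 days after Treatment Visit 4. That fits Cohort 1 (3 × 14 + 42 = 84) but not Cohort 2 (3 × 21 + 42 = 105, neither its EOT nor its EOS).

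This is probably how the text arose, and it limits how often harm is likely. It does not remove the defect. Section 4.4 labels the wart count as Cohort 1 in the same paragraph and names Cohort 2 in the next; section 6.1 names both cohorts for the Day 63 and Day 75 limits. An unlabelled sentence among labelled ones reads as applying to both. The reply also leaves the 17-day versus 21-day conflict untouched, since both of those statements name Cohort 2.

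A reader might infer that a 17–20 day interval is a dosing error and so leads to Per Protocol exclusion. The documents do not support that. The dosing-error criterion is in the SAP, which itself states 17 days, and the SAP has major deviations decided by clinical review before anyone is excluded. The protocol's own list of exclusions has no interval item.

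A reader might also want a rate of such departures, by assuming how intervals spread over the window. The documents give no distribution, visits are targeted at 21 days and delayed for skin reactions, and not every subject has three re-treatments. No rate can be given.

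**Conclusion.** The inconsistency is real and sits in current operative text. Two consequences follow. First, an interval of 17–20 days is compliant under section 4.1 and the SAP but not under section 5.2, to which 8.1.3 refers. Discontinuation there is permitted after consultation, not automatic. Second, a cleared Cohort 2 subject followed by phone is scored not cleared at one or two interim windows, at about 2.9 points per subject per window, and could be excluded from the Per Protocol population for missed required visits.

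This rests on three assumptions: 35 subjects in the denominator, a site acting on the unlabelled text, and no wart form completed from a phone call. The number of subjects affected cannot be derived; it is zero if every site follows section 4.1.

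A reader might infer that cleared subjects would count as failures on the primary endpoint. They would not, because the Day 84 visit stays in person, as do the later Cohort 2 follow-up visits. The effect is confined to secondary and exploratory by-visit results and the Per Protocol set, in a descriptive study with no formal comparison. It should be corrected but does not threaten the main result.

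**What to change.** The sponsor should reconcile protocol sections 4.1, 4.4, 5.2 and 6.1, the synopsis and the SAP to one stated Cohort 2 interval and one follow-up rule for cleared Cohort 2 subjects. This review does not say which interval or rule is right. Where the 14-day and phone-call sentences in 4.4 and 6.1 are meant for Cohort 1 only, they should say so. The deviation review and the Per Protocol rules should cite the reconciled interval, and the reference to Section 5 in 8.1.3 will then point to the same figure. The cost is protocol and SAP wording and a clarification to at most four sites; no new data or analyses are needed.
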